8.3 Drug Dispensing

Identical-appearing creams and pills will be packaged and distributed by Central Compounding Pharmacy to the UNC site, and by the Pacifica Compounding Pharmacy to the UCLA site. At the baseline visit, participants will receive a sufficient supply of study drug for weeks 1-8, and some (3 days) extra in the event of delay in scheduling visit 2. At the 8-week visit, participants will receive a sufficient supply of study drug for the remaining weeks 9-16, and some (3 days) extra in the event of delay in scheduling visit 3. Patients will be instructed to take the medication as required by the protocol.

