8.5 Drug Accountability

Participants are instructed to return all used, partly used and unused trial products (study drugs and packaging material) at each study visit. Returned trial product(s) must be stored separately from the non-allocated trial product(s) until drug accountability has been reconciled. The respective clinical investigators will be responsible for monitoring all received, used, partly used and unused trial product(s).

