8.6 Drug Destruction

Used and unused study drug will be returned to the respective compounding pharmacies for destruction according to accepted pharmacy practice and both local and national guidelines. A

copy of the drug destruction procedure should be maintained in the pharmacy section of the Regulatory Binder. Study drug destruction should be documented in the comments section of the Subject Specific Drug Accountability Log.

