11 FOLLOW-UP EVALUATIONS

11.1 Visit 2 (8-Week)

Upon arrival, participants will return any remaining study medication to the research team.

The week 8 visit procedures and assessments will be performed in the following order:

- Tampon test with 0-10 NRS
- Blood collection and processing
- Participant questionnaires:

- VPAQ
- PROMIS BPSFS-F
- COPC follow-up survey
- SF12v2
- SCL-27
- PILL
- PSS
- Sleep scale
- Remote bodily PPTs (deltoid, shin, trapezius)
- Qualitative pelvic sensory testing
- Vaginal sample collection
- Local vestibular PPTs (5, 6, and 7 o'clock)

At the end of visit 2, participants will receive a sufficient supply of study drug for weeks 9-16. Patients will be instructed to take the medication as required by the protocol and complete a daily medication diary.

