20 APPENDICES

Appendix A. Schedule of Assessments

Assessment	Screening (0 week)	Baseline Visit (0 week)	Treatment Visit (8 week)*	Treatment Visit (16 week)**	Post-treatment (24 week)***
Patient Consent	X ^{FS}				
Tampon Test	X ^{FS}		X	X	X
Pain with sexual contact involving penetration into the vagina	X		X	X	X
Pain with touch to the vaginal opening	X		X	X	X
Blood Collection		X ^{FS}	X	X	X
Demographics		X ^{FS}			
Social History		X ^{FS}			
Gynecologic History		X ^{FS}			
VPAQ		X ^{FS}	X	X	X
PROMIS BPSFS-Female		X ^{FS}	X	X	X
COPC Inventory		X ^{FS}			
COPC Follow-Up			X	X	X
SF-12v2		X ^{FS}	X	X	X
SCL-27		X ^{FS}	X	X	X
PILL		X ^{FS}	X	X	X
PSS		X ^{FS}	X	X	X
Sleep Scale		X ^{FS}	X	X	X
Vaginal Sample Collection		X ^{FS}	X	X	X
Pelvic Sensory Testing		X ^{FS}	X	X	X
Vaginal Vestibule PPTs		X ^{FS}	X	X	X
Perineal Muscle PPTs		X ^{FS}	X	X	X
Levator Muscle PPTs		X ^{FS}	X	X	X
Remote Bodily PPTs		X ^{FS}	X	X	X
Medication Compliance			X	X	

FS = assessments collected for the feasibility study

[figure not shown]
X = assessments collected for the full study

*8 weeks (56 days) following randomization, +/- 5 days

**16 weeks (112 days) following randomization, +/- 5 days

***24 weeks (168 days) following randomization, +/- 5 days

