Appendix D. Medication Calendar

Medication Calendar

Please complete the survey below.

Thank you!

Please select the date you started your study medication.

Can you please confirm the day of the week you started your medication?

- ☐ Sunday
☐ Monday
☐ Tuesday
☐ Wednesday
☐ Thursday
☐ Friday
☐ Saturday

The questions below will ask about your daily use of the prescribed medication for the first two months following your initial study visit. If, for example, begin your medication on a Wednesday, you will need to complete your responses into Wednesday of Week 9.

	Cream Applied: No	Cream Applied: Yes	Pills taken: 0	Pills taken: 1	Pills taken: 2	Pills taken: 3	Pills taken: 4	Pills taken: 5	Pills taken: 6
Week 1: Sunday									
Week 1: Monday									
Week 1: Tuesday									
Week1: Wednesday									
Week1: Thursday									
Week1: Friday									
Week1: Saturday									

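### The 3 spare days of study drug do not cover the 5-day delay the schedule allows, so a fully adherent woman can be 1-2 days without drug before an in-window visit 2 or visit 3

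*Combined protocol and SAP*

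**What the plan says.** Section 8.3 describes two dispensings. At baseline a woman receives a "sufficient supply of study drug for weeks 1-8, and some (3 days) extra in the event of delay in scheduling visit 2"; at week 8 she receives a "sufficient supply of study drug for the remaining weeks 9-16, and some (3 days) extra in the event of delay in scheduling visit 3". Sections 10.2 and 11.1 restate the two supplies as covering weeks 1-8 and weeks 9-16 and mention no spare days.

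The visit windows are in the footnotes to Appendix A. Visit 2 is "8 weeks (56 days) following randomization, +/- 5 days" and visit 3 is "16 weeks (112 days) following randomization, +/- 5 days".

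Drug does not carry over between dispensings. Section 8.5 says "Participants are instructed to return all used, partly used and unused trial products (study drugs and packaging material) at each study visit", section 8.6 adds "Used and unused study drug will be returned to the respective compounding pharmacies for destruction", and section 11.1 says of visit 2 "Upon arrival, participants will return any remaining study medication to the research team". In section 11.1 the tampon test is the first procedure and new drug is given at the end of the visit.

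Section 8.1 plans daily cream for 16 weeks, and nightly pills rising to five from week 5 and then tapered over weeks 16-18. Section 11.2 has study medication discontinued at visit 3. The first-dose date is recorded separately from randomization: the calendar in Appendix D asks "Please select the date you started your study medication".

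**The concern.** The spare drug has one stated purpose, to cover a late visit, and it is two days shorter than the lateness the schedule permits. A woman can follow every instruction, attend within the window, and still arrive untreated for a day or two.

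The measurements concerned are the week-16 tampon score (a primary endpoint of Aim 1), the week-8 pain scores (secondary, and part of the longitudinal outcome modelled in section 15.2), and the week-8 and week-16 cytokine and microRNA samples. New drug at visit 2 comes after the tampon test, so it cannot close a gap before that test. A woman on 50 mg of nortriptyline who runs out would also stop abruptly, whereas section 8.1 plans a stepwise taper.

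**Working it through.** **Inputs.** Supply per dispensing: 8 weeks plus 3 days (section 8.3). Windows: day 56 and day 112, each +/- 5 days (Appendix A). Dosing: daily cream, nightly pills (section 8.1).

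**The plan's own figures.** 8 x 7 = 56 and 16 x 7 = 112 reproduce the nominal visit days. The windows are therefore days 51-61 and days 107-117.

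**Conventions (assumed).** Day 0 is randomization. The visit-day dose is taken after the visit. Every dose is taken at full dose. The second supply runs to the end of week 16 plus 3 days.

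**Visit 2.** Supply = 56 + 3 = 59 days. Days without drug = max(0, visit day - first-dose day - 59). With a first dose on day 0 the last dose is on day 58. Day 60 gives 60 - 0 - 59 = 1 and day 61 gives 61 - 0 - 59 = 2.

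**Visit 3.** Supply reaches 112 + 3 = 115 days from the first dose. Days without drug = max(0, visit day - first-dose day - 115). With a first dose on day 0, day 116 gives 1 and day 117 gives 2.

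| First dose | Visit 2, day 60 | Visit 2, day 61 | Visit 3, day 116 | Visit 3, day 117 |
|---|---|---|---|---|
| day 0 | 1 | 2 | 1 | 2 |
| day 1 | 0 | 1 | 0 | 1 |
| day 2 | 0 | 0 | 0 | 0 |

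Every other in-window day gives 0. At most 2 of the 11 permitted days at each visit are affected. This counts possible dates; it is not an expected frequency.

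**Where the gaps fall.** Days 59 and 60, before visit 2, lie inside the planned daily course. Days 115 and 116, before visit 3, lie after the nominal 112-day course.

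**Check of the remedy.** With 61 days at baseline, the gap at day 61 is 61 - 0 - 61 = 0. With a visit 2 supply of 117 minus the visit 2 day, the last dose is on day 116 and the gap at day 117 is 0. On schedule that supply is 117 - 56 = 61 days.

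**The case against.** The strongest reply is that the two provisions can coexist. Section 8.3 promises some extra drug and never says that it spans the whole window, while Appendix A sets a tolerance for assessments. That is fair as a matter of wording. But section 8.3 names delayed visits as the reason for the extra days, and a buffer shorter than the permitted delay does not do that job.

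The second reply is that section 8.1 ends cream at 16 weeks, so a woman seen on day 116 or 117 is past the planned course. This stands in part: on the reading used here, no planned dose is missed after visit 2. It does not touch visit 2. At visit 3, section 8.3 supplies drug for a delayed visit and section 11.2 stops drug at the visit, so dosing up to the visit appears to be intended.

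The third reply is that the gap may not occur at all. No cream container size is given, so cream may last longer. A woman on a reduced dose has pills left. If taper pills were dispensed at visit 2, the 40 needed from 50 mg would equal 40 / 5 = 8 full-dose days and would cover a pill gap before visit 3. All of this stands, and it makes the gap possible, not certain.

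Three stronger readings are tempting. A reader might infer a longer gap before visit 3 by treating the second supply as a fixed number of days counted from an early visit 2. Section 8.3 speaks of the weeks remaining up to week 16, which points to an end date. A reader might also infer from sections 10.2 and 11.1 that no spare days are dispensed; those sections are better read as summaries of section 8.3. Finally, a reader might infer that the week-16 comparison is biased. Supply and windows are the same in all four arms, the analysis is by intention to treat, and the documents give neither visit-timing data nor a rate at which the effect wanes.

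**Conclusion.** The mismatch is real and small. Under the stated conventions a fully adherent woman at full dose can be without drug for 1 or 2 days before an in-window visit 2, within her planned course. The same can happen before an in-window visit 3, after the nominal course but within the delay that the spare drug was meant to cover. It requires a first dose on day 0 or day 1, a visit in the last one or two days of the window, and no leftover product. Frequency and effect on the results cannot be estimated, and no power or sample size figure changes. It is a cheap improvement, worth making because it changes what a woman receives just before an efficacy measurement.

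**What to change.** In sections 8.3, 10.2 and 11.1, dispense 61 days at baseline and, at visit 2, enough to reach day 117 (117 minus the visit 2 day; 61 days on schedule). In sections 8.1 and 11.2, state that cream and pills continue to the actual visit 3 and that the pill taper starts then. Supply the taper pills at visit 3: from 50 mg, 4 x (4 + 3 + 2 + 1) = 40 pills.

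Costs:
- Product for a woman on schedule rises from 59 + 59 = 118 to 61 + 61 = 122 days, which is 4 days (+3.4%), or 4 x 5 = 20 pills at full dose.
- Returns on schedule rise from 3 to 5 days at each of visits 2 and 3 (61 - 56 and 117 - 112). The most that could come back at visit 3 is 117 - 107 = 10 days.
- Treatment lasts up to 117 - 112 = 5 days beyond 16 weeks when visit 3 is late.
- A protocol amendment is needed. Because treatment duration can change, it is not purely administrative and needs IRB approval under section 18.2.

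No visit, procedure or data field is added. The alternative is to shorten the late side of both windows to +3 days. That needs no extra drug, but more visits would fall out of window, and the documents do not show how many.

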8.4 Drug Storage

The study drug should be stored at controlled room temperature 15°-30°C (59°-86°F) and will be dispensed in a light-resistant container. Excessive moisture should be avoided. Study drug must be kept out of reach of children.

8.5 Drug Accountability

Participants are instructed to return all used, partly used and unused trial products (study drugs and packaging material) at each study visit. Returned trial product(s) must be stored separately from the non-allocated trial product(s) until drug accountability has been reconciled. The respective clinical investigators will be responsible for monitoring all received, used, partly used and unused trial product(s).

8.6 Drug Destruction

Used and unused study drug will be returned to the respective compounding pharmacies for destruction according to accepted pharmacy practice and both local and national guidelines. A

copy of the drug destruction procedure should be maintained in the pharmacy section of the Regulatory Binder. Study drug destruction should be documented in the comments section of the Subject Specific Drug Accountability Log.

8.7 Randomization and Blinding

Drug assignments will be determined by the DCRI using randomized blocks, and then stratified by enrollment site. The DCRI will create a SAS program to generate the random sequence that will be loaded in REDCap.

Participants and research personnel will be blinded to medication assignment. Blinding of the study, with respect to treatment groups will be preserved by the use of placebo cream and capsules that are identical in appearance to the active study drugs. Investigators may be asked at the end of the trial if he/she had obtained any information that may have led to the potential unblinding of treatment.

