5.3 Baseline Evaluation Phase and Randomization

Immediately following screening, research participants will complete all baseline assessments, including 1) completion of validated questionnaires to measure perceived pain, health, mood, and sexual function 2) vulvar exam and quantitative sensory testing to measure pressure pain thresholds at local (vaginal) and remote body sites, and 3) collection of biologic samples to measure local (vaginal) and systemic (blood) cytokines and miRNAs. The complete schedule of assessments to be obtained during the baseline visit is outlined in **Appendix A**.

Participants who fulfill all the inclusion criteria and none of the exclusion criteria will be randomly assigned on a 1:1:1:1 ratio to one of four treatment groups:

- 5% lidocaine/0.5mg/ml 0.07% estradiol compound vaginal cream + placebo pill
- placebo vaginal cream + nortriptyline pill
- 5% lidocaine/0.5mg/ml 0.07% estradiol compound vaginal cream + nortriptyline pill
- placebo vaginal cream + placebo pill

Medication assignments will be determined by the Duke Clinical Research Institute (DCRI) using randomized blocks, and then stratified by enrollment site. The DCRI will create a SAS program to generate the random sequence that will be loaded in RedCap. Participants and research personnel will be blinded to medication assignment.

[figure not shown]
During the baseline visit, participants will be counseled on optimal study medication administration. Participants will receive a written description of the study with contact numbers of study staff to present to their usual care provider(s).

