9.2 Estimated Enrollment Period

Each site will screen for eligible participants to achieve a target of 200 randomized participants per site. We expect to randomize an average of 4-5 participants per month per study site beginning in the second quarter of funding Year 2. At that rate, the final (400th) participant will be randomized at the end of Year 5. This projected rate of randomization is readily achievable based on current patient volume at UNC and UCLA (151 and 101 new patients per year, respectively), which is expected to increase with utilization of our recruitment methods.

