10.2 Drug Dispensing

All eligible study participants who successfully complete screening and baseline evaluations will be randomized (as detailed in **Section 8.7**) to receive one of four types of medication kits:

- 5% lidocaine/0.5mg/ml 0.07% estradiol compound vaginal cream + placebo pill
- placebo vaginal cream + nortriptyline pill
- 5% lidocaine/0.5mg/ml 0.07% estradiol compound vaginal cream + nortriptyline pill
- placebo vaginal cream + placebo pill

Identical-appearing creams and pills will be packaged and distributed by the Central Compounding Pharmacy to UNC and by the Pacifica Compounding Pharmacy to UCLA. At the baseline visit, participants will receive a sufficient supply of study drug for weeks 1-8. Patients will be instructed to take the medication as required by the protocol and complete a daily medication calendar (**Appendix D**).

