15 STATISTICAL CONSIDERATIONS

15.1 VBD Subtype Designation

Women with VBD-c will be distinguished from those with VBD-p based on the presence of a COPC. The Institute of Medicine's 2011 report, *Relieving Pain in America*, identified 9 COPCs that predominantly affect women and frequently co-occur with VBD.⁹³ The presence of a COPC will be determined using the COPC survey. This is an easy-to-complete form including modules with check-box questions and a body mannequin to determine the presence of 9 COPCs: 1) FMS, 2) TMD, 3) back pain, 4) IBS, 5) chronic tension-type headache, 6) chronic migraine, and 7) chronic fatigue syndrome, 8) endometriosis, and 9) interstitial cystitis. Women with VBD and no COPCs will be designated as VBD-p, while women with VBD and ≥ 1 COPC will be designated as VBD-c. These criteria will be used as a primary method to distinguish between VBD-p and VBD-c in this study.

We, however, acknowledge that the criteria to distinguish VBD subtypes needs further exploration. In particular, it is possible that the optimal cutoff for VBD-c requires more than one COPC to be present. Therefore, as a secondary method to characterize VBD subtypes, we will calculate a continuous COPC 'centralness' score defined as the number of COPCs present ranging from 0 to 9. This continuous COPC score will be used to identify the optimal cutoff value between VBD-p and VBD-c in terms of treatment response.

To further characterize the two VBD subtypes, we will also measure generalized pain at 'neutral' non-pelvic sites using a quantitative sensory testing approach designed by [name] and colleagues.^{94, 95} The 3 neutral sites (deltoid muscle, shin, trapezius) are remote from the pelvic region and not used for diagnosing other pain conditions, but reflect an individual's overall

pressure pain sensitivity.⁹⁸⁻¹⁰⁰ An algometer will be applied to the 3 sites, with continuously ascending pressure at a rate of 1 kg/s to a maximum of 10 kg. Participants will indicate when the evoked sensation first becomes painful. A composite pressure pain threshold (PPT) score will be compared between VBD-c and VBD-p subgroups using ANCOVA. We would expect women with VBD-p to have higher PPT scores (less pain) and women with VBD-c to have lower scores (more pain) at these sites.

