15.6 Sample Size and Power

We are planning to enroll 400 women with VBD, with an estimated attrition rate of 20%. Of note, Reed et al. found that vulvar pain measured on a 0-10 numeric scale has standard deviation 2.0.¹⁰⁴ Salaffi et al¹⁰⁵ noted that 2 points on a 0-10 NRS correspond to a clinically meaningful difference in pain severity. Using these results and assuming the within-subject correlation of 0.5, at a significance level of 0.05, the proposed sample size will provide sufficient power of at least 0.80 to detect differences as small as 0.82 on a 0-10 scale for the overall treatment main effects (3 arms) vs. placebo. To test each individual treatment effect vs. placebo, at a significance level of 0.0167 (Bonferroni-corrected for 3 arms), the proposed sample size can detect differences as small as 0.98 on a 0-10 scale. At a significance level of 0.05, the proposed sample size can detect differences as small as 1.35 and 1.20 on a 0-10 scale for the interaction effect of treatment and each VBD-subtype, given possible splits of 40/60, 50/50, or 60/40 (of note, VBD-p vs VBD-c frequencies were 40/60 at UNC and 50/50 at UCLA clinics in previous studies).

To calculate power for research question IIIa, we used data from our previous study of biomarkers in VBD patients.⁷ Conservatively assuming that VBD-c patients represent 60% (192/320) of the sample and VBD-p patients represent 40% (128/320) of the sample, and adjusting the significance threshold for 4 tier 1 cytokine tests, we will be able to detect mean differences of at least 0.4 SD with the power of 0.84 or greater using a t-test. For IL-8, 0.4 SD translates to approximately 2 pg/mL, and for IL-1ra 0.4 SD translates to 240 pg/mL of the minimal detectable difference. Of note, the mean differences between controls and VBD patients for IL-8 and IL-1ra in our previous study were 4 pg/mL and 300 pg/mL, respectively. Thus, we have sufficient power to detect plausible differences in cytokine levels between the VBD subgroups.

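### Minor, cheap improvement: stratify randomisation by VBD subtype as well as site, because questions 1b and 2b rest on arm-by-subtype cells that are now left to chance

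*Combined protocol and SAP*

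**What the plan says.** Sections 5.3 and 8.7 agree on the allocation. Section 5.3 has women "randomly assigned on a 1:1:1:1 ratio to one of four treatment groups", and continues: "Medication assignments will be determined by the Duke Clinical Research Institute (DCRI) using randomized blocks, and then stratified by enrollment site". Section 8.7 repeats it: "Drug assignments will be determined by the DCRI using randomized blocks, and then stratified by enrollment site". No section names subtype as a stratum, and no block size is given.

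Section 9.2 asks each site "to achieve a target of 200 randomized participants per site", so the total is 400. Section 15.6 assumes 20% attrition.

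Subtype is a count from the COPC survey. Section 15.1 says: "Women with VBD and no COPCs will be designated as VBD-p"; one or more COPCs makes a woman VBD-c. The COPC inventory is among the baseline questionnaires (Section 10.1 and Appendix A). Randomisation comes afterwards (Section 10.2): "All eligible study participants who successfully complete screening and baseline evaluations will be randomized".

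In Section 15.2, question 1b asks whether peripheral treatment beats central treatment in VBD-p, and the reverse in VBD-c. Question 2b in Section 15.3 asks the same for health outcomes. Both are tested through treatment-by-subtype terms, followed by comparisons of LS means in treatment-by-subtype subgroups. The model for question 1a pools the subtypes and carries subtype as a covariate.

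**The concern.** Blocking within site keeps the four arms equal in size at each site. It does not keep the number of VBD-p women equal across arms. Questions 1b and 2b depend on eight cells (four arms by two subtypes), and the precision of a within-subtype contrast is governed by the smaller of the two cells compared. Adjusting for subtype removes the confounding that a chance imbalance would cause, but it cannot replace women missing from a small cell. What is at stake is some precision for 1b and 2b, and arms that look unbalanced on the trial's main effect modifier. Since the information needed to prevent this is collected before allocation, the loss is avoidable.

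**Working it through.** **1. The plan's own subtype figures.** Section 15.6 states detectable differences of 1.35 and 1.20 points. Its inputs are "vulvar pain measured on a 0-10 numeric scale has standard deviation 2.0", within-subject correlation 0.5, alpha 0.05 and power 0.80.

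- SD of change = 2.0 × √(2 × (1 − 0.5)) = 2.0.
- Women per arm at week 16, if the 20% attrition accrues linearly to week 24 (an assumption): 100 × (1 − 0.20 × 16/24) = 86.7.
- Active versus placebo within one subtype: (1.960 + 0.842) × 2.0 × √(2/(86.7 × share)). This gives 1.35 at a 40% share and 1.20 at 50%, matching the plan. With 80 completers per arm it gives 1.40 and 1.25.
- A difference of differences adds 2/(86.7 × (1 − share)) under the root. This gives 1.74 at 40/60 and 1.70 at 50/50.

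The stated figures therefore reproduce as within-subtype differences, although Section 15.6 labels them as interaction effects. That is a separate matter. It bears on this point only because it shows little precision to spare for 1b and 2b.

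**2. Expected cell size.** At 40/60 overall, VBD-p women per arm = 400 × 0.40 / 4 = 40. At the frequencies quoted for the two clinics (40% at UNC, 50% at UCLA), it is (200 × 0.40 + 200 × 0.50) / 4 = 45.

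**3. Chance variation without a subtype stratum.** Take four arms of 100 and 160 VBD-p women allocated at random.

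- SD of one arm's VBD-p count = √(100 × 0.4 × 0.6 × 300/399) = 4.25.
- Variance relative to balance, for arms with a and b VBD-p women:
  - within VBD-p: (1/a + 1/b) / (2/40)
  - interaction: (1/a + 1/b + 1/(100−a) + 1/(100−b)) / (2/40 + 2/60)
- Example with a = 31, b = 40: within VBD-p, (0.03226 + 0.02500)/0.0500 = 1.145; interaction, 0.08842/0.08333 = 1.061.

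Multivariate hypergeometric simulation (20,000 draws; a repeat with 200,000 agreed) gives:

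| Quantity | Result |
|---|---|
| Smallest of the four VBD-p cells, mean | 35.0 |
| Smallest cell 31 or fewer | about 9% of trials |
| Interaction variance inflation: mean, 95th percentile | about 1%, about 5% |
| Within-VBD-p two-arm inflation: mean, 95th percentile | about 1%, about 12% |

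With 320 women the two 95th percentiles become about 6% and 14%.

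**4. What stratifying would change.** This used 4,000 simulated trials per scenario, 200 women per site, random 20% dropout, and assumed block sizes of 4 and 8. VBD-p share was 40% at UNC and 50% at UCLA.

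| Quantity | Site only | Site × subtype |
|---|---|---|
| Largest arm-to-arm gap in VBD-p share, median | 10 points | about 1 point |
| Same, 95th percentile | 17–18 points | 1.6–2.4 points |
| VBD-p women per arm, 95% range | 36–55 | 40–50 |
| Mean detectable interaction | 1.794 | 1.788 |
| Power, interaction of 1.75 | 0.780 | 0.783 |
| Power, within-VBD-p difference of 1.35 | 0.81 | 0.81 |

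With 40% VBD-p at both sites, within-VBD-p power at 1.35 rises from 0.762–0.764 to 0.767, and interaction power at 1.75 from 0.767 to about 0.770.

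**The case against.** The case for leaving the design alone is strong on size. Subtype is a fixed effect in model 1a and is crossed with treatment in model 1b, so imbalance is adjusted for. A 1% variance inflation widens an interval by about 0.5%. Even the 5% figure widens it by only √1.05 = 1.025. The expected 40 per arm is one of several splits that Section 15.6 allows, and the stated clinic frequencies give 45. Stratifying does not fix cell sizes, because the total number of VBD-p women stays random. All of this stands, and it is why the point is minor.

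Section 15.1 also treats the subtype cutoff as provisional and plans to look for a better one. Strata set at no COPC versus at least one would not specifically balance the arms at another cutoff. That limits the benefit, but it does not make balance at another cutoff worse, and this cutoff is the plan's primary definition.

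Two stronger readings are not supported:

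- A reader might infer that every primary question depends on these cells. Question 1a is worded by subtype but its model pools subtypes. Questions 2a and 3a are baseline associations that do not use the allocation, and 3b concerns treatment by biomarker. Only 1b and 2b rest directly on the arm-by-subtype cells.
- A reader might infer that subtype is already known at allocation. The documents show that the inventory is completed by then, not that it is scored.

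**Conclusion.** The point holds as a low-cost improvement, not as a flaw in validity. Allocation ignores the variable that questions 1b and 2b are about, although its source data are in hand beforehand. The models include subtype, so no bias follows, and the average gain from stratifying is about 1% of variance and at most about 0.5 percentage points of power. What it buys is protection against a poor draw: at the 95th percentile, the variance of a two-arm contrast within VBD-p is about 12% above its balanced value, an interval about 6% wider (√1.12 = 1.058).

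The cell figures assume 400 women and a 40/60 split. The power comparison assumes block sizes of 4 or 8 and dropout unrelated to arm or subtype.

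**What to change.** Stratify the REDCap sequence by site and VBD subtype, using the plan's primary definition (no COPC versus at least one). State in Sections 5.3 and 8.7 that the COPC inventory is scored before allocation. This makes four strata of roughly 80 to 120 women (200 × 0.40 = 80; 200 × 0.60 = 120), so over-stratification is not a concern.

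The costs are new randomisation lists and same-day scoring of the inventory. A scoring error would put a woman in the wrong stratum. Arms would not be specifically balanced at an alternative COPC cutoff, and the total number of VBD-p women would still vary. The change helps only women not yet randomised; if enrolment is complete, report the eight cell sizes.
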